#### Confidentiality Statement

This document is the property of Worldwide Clinical Trials Inc. and may not be duplicated, copied, altered or removed from company without prior approval from Worldwide Quality Assurance or in compliance with Worldwide Standard Operating Procedures.

Worldwide Clinical Trials Controlled Quality Management Document			
 WORLDWIDE CLINICAL TRIALS	Sponsor:	Flamingo Therapeutics	Protocol Number:
STATISTICAL ANALYSIS PLAN			

Study Objects and Endpoints	
Exploratory Objectives	Exploratory Endpoints

 
To determine the pharmacodynamic activity of danvatirsen in pre- and on-treatment tumor and blood specimens
 
To determine the relationship between clinical activity and human papillomavirus (HPV) and other biomarkers in pre- and on-treatment specimens
 
	
 
STAT3 levels and protein levels in pre- and on-treatment samples
 
Gene expression changes (RNA and/or protein) in pre- and on-treatment samples
 
Determination of HPV positivity
 

### 3 SAMPLE SIZE

Sample size considerations were based on monitoring the primary efficacy endpoint, ORR, using a 2-arm Bayesian optimal phase 2 (BOP2) design.

The primary efficacy evaluation will be the magnitude of ORR in each of the treatment arms and the probability that the combination arm ORR is superior to that of the control (monotherapy) arm, that is  $\text{Pr}(\text{ORR}_{\text{comb}} > \text{ORR}_{\text{con}} | \text{data})$ .

The design is optimized to maximize the power under  $H_0$ :  $\text{ORR}_{\text{con}} = 0.15$  and  $\text{ORR}_{\text{comb}} = 0.43$ , while controlling the type I error rate at 1-sided 0.05.

An interim futility analysis is planned when ORR can be assessed for the first 39 patients, and the final ORR analysis is planned after 81 patients are followed for a minimum of 3 months (2 radiologic scans). A 2:1 combination: control randomization will be used for the 2 arms and will yield 83% power at the 1-sided 5% alpha based on the decision rule to reject the null hypothesis and conclude that the combination arm is superior compared to the control.

### 4 RANDOMIZATION

Upon confirmation of eligibility, patients will be randomized in a 2:1 ratio to either Danvatirsen + pembrolizumab or Pembrolizumab monotherapy.

Study randomization will be managed centrally through an Interactive Response Technology (IRT) system. Sites will receive the randomized treatment assignment for all patients by logging into the IRT system and entering the required data.

Randomization will be stratified by Eastern Cooperative Oncology Group (ECOG) performance status (0 vs. 1) for patients enrolled under the original protocol or Amendment 1. For patients enrolled under Amendment 2 or later, randomization will be stratified by CPS ( $1 \leq \text{CPS} < 20$  vs  $\text{CPS} \geq 20$ ). The change in stratification variables will not impact the intended randomization balance.

QMD Ref: Worldwide-TMP-ST-054-1.0_Effective: 12Aug2022	Governing QMD: Worldwide-SOP-ST-026
Confidentiality Statement	
This document is the property of Worldwide Clinical Trials Inc. and may not be duplicated, copied, altered or removed from company without prior approval from Worldwide Quality Assurance or in compliance with Worldwide Standard Operating Procedures.	

Worldwide Clinical Trials Controlled Quality Management Document			
 WORLDWIDE CLINICAL TRIALS	Sponsor:	Flamingo Therapeutics	
	Protocol Number:	FLM-6774-201	
STATISTICAL ANALYSIS PLAN			

A Tumor Proportion Score (TPS) value  $\geq 30$  may be used for initial eligibility. The subject will be assigned to the  $1 \leq \text{CPS} < 20$  stratum, if  $30 \leq \text{TPS} < 50$ , or the  $\text{CPS} \geq 20$  stratum, if  $\text{TPS} \geq 50$ . However, a CPS value must be obtained and reported utilizing a tissue sample obtained prior to the start of study treatment.

Blinding is not applicable for this open-label study.

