3.4 Randomization and Blinding

Randomization will be managed centrally through an Interactive Response Technology (IRT) system. Patients will be randomized in a 2:1 ratio to either danvatirsen + pembrolizumab or pembrolizumab monotherapy. Randomization will be stratified by Eastern Cooperative Oncology Group (ECOG) performance status (0 vs. 1 [Appendix 1]) for patients enrolled under the original protocol or Amendment 1.

For patients enrolled following this amendment, randomization will be stratified by the CPS (CPS ≥ 1 and < 20 vs. CPS ≥ 20) obtained during screening, instead of ECOG performance status. Considering the addition of the new subgroup of subjects (CPS ≥ 1 and < 20) as of this amendment, the change in stratification variables will not impact the intended randomization balance. Removing ECOG performance status as a potential second stratification variable in addition to CPS is necessary considering the limited size of the study and the 2:1 randomization ratio.

Flamingo Therapeutics

Activity and Safety of Danvatirsen and Pembrolizumab in HNSCC

8 May 2025

Trial ID: FLM-6774-201

Amendment 4

Sites will receive the randomized treatment assignment for all patients by logging into the IRT system and entering the required data.

Patients who are randomized in the IRT but do not receive study treatment will not be replaced.

Blinding is not applicable for this open-label study.

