Table 10: Operating Characteristics

Scenario	% ORR Control	% ORR Combination	Early Futility Stopping (%)	Claim Promising (%)	Average Sample Size
1	15	15	46.1	4.6	62
2	23	23	43.8	4.5	63
3	20	40	7.1	54.6	78
4	23	43	7.7	52.9	78
5	25	50	4.5	68.6	79
6	15	43	1.9	82.7	80

Abbreviation: ORR = objective response rate

Additional futility monitoring criteria will be taken into consideration for the subgroup of patients with CPS ≥ 1 and < 20 . Specifically, if no more than one patient achieves a response (confirmed or unconfirmed CR or PR within the first two scans) in the first 10 patients enrolled in the combination arm for this subgroup, there will be no further enrollment in this subgroup, and the study will continue to enroll in the CPS ≥ 20 subgroup, consistent with any guidance based on the monitoring criteria outlined in [Table 9](#). Additionally, accrual in the CPS ≥ 1 and < 20 subgroup will pause, if no responses have been achieved, but response data for the first 10 patients in that subgroup are not yet mature, defined as at least 2 scans assessed.

Considering the limited size of the CPS ≥ 1 and < 20 subgroup, the futility criteria were derived based on a single arm BOP2 design with the interim assessment after 10 patients, a final assessment of 27 patients (half of the intended size of the combination arm) testing a null hypothesis of 15% ORR (KEYNOTE-048 pembrolizumab monotherapy ORR for this subgroup ([Burtness et al 2022](#))) vs. an alternative hypothesis of 29% ORR (SCORES combination arm for this subgroup), at 1-sided 10% level with approximately 65% power.

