### 5.3 Randomization Strata

Randomization will be stratified by Eastern Cooperative Oncology Group (ECOG) performance status (0 vs 1) for patients enrolled under the original protocol or Amendment 1. For patients enrolled under Amendment 2 or later, randomization will be stratified by CPS ( $1 \leq \text{CPS} < 20$  vs  $\text{CPS} \geq 20$ ). The change in stratification variables will not impact the intended overall randomization balance.

A TPS value  $\geq 30$  may be used for initial eligibility. The subject will be assigned to the  $1 \leq \text{CPS} < 20$  stratum, if  $30 \leq \text{TPS} < 50$ , or the  $\text{CPS} \geq 20$  stratum, if  $\text{TPS} \geq 50$ . However, a CPS value must be obtained and reported utilizing a tissue sample obtained prior to the start of study treatment.

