#### 5.12.4.3 Progression Free Survival

PFS is defined as the time from date of randomization to first progression of disease (PD) or death due to any cause, whichever occurred first, where the disease progression will be determined based on RECIST v1.1 criteria. The analysis of this endpoint will be based on FAS population.

$$PFS \text{ (Months)} = \frac{(Date \text{ of } PD \text{ or Death or Censoring} - Date \text{ of randomization}) + 1}{30.4375}$$

PFS may be censored to a stop date other than PD or death, as described in the censoring rule table of [Section 5.12.4.5](#).

PFS median follow-up time (MFT) is defined as the time from date of randomization until the time where a subject is censored based on censoring rules for PFS. In the calculation for PFS MFT, documented PD or death will be considered censored events, rather than events.

Kaplan-Meier estimates of 25th, 50th and 75th percentiles for PFS and PFS MFT will be presented. Corresponding 95% confidence intervals using Greenwood's formula will be provided. Minimum and Maximum PFS will be presented.

A Stratified Log-Rank test will be conducted, stratified for Baseline CPS category, to compare both treatment arm and the p-value will be provided. The following SAS code will be used:

```
ods output homtests=<outdata>;
proc lifetest data=adtte;
  time aval*cnsr(1);
  strata cpsgr1 / group=trt01pn;
run;
```

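### The SAP places patients entering on TPS 30 to under 50 in the CPS 1 to under 20 stratum, contrary to the protocol's stratification on screening CPS, and leaves open which CPS value the subgroup futility count and CPS analyses use

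*SAP*

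**What the plan says.** **Stratum rule in the SAP.** Section 4, repeated in section 5.3, says that a TPS of at least 30 "may be used for initial eligibility. The subject will be assigned to the" 1 to under 20 CPS stratum when TPS is 30 to under 50, and to the CPS 20 or higher stratum when TPS is 50 or more. No reason is given for these cut-points. Both sections then add: "However, a CPS value must be obtained and reported utilizing a tissue sample obtained prior to the start of study treatment". This dates the tissue sample. It sets no deadline for the CPS result, and no rule covers a result that disagrees with the assigned stratum.

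**Stratum rule in the protocol.** Section 3.4 stratifies on the CPS "obtained during screening, instead of ECOG performance status". Inclusion criterion 5 lets a TPS of 30 or more serve for initial eligibility only. The protocol has no TPS-to-stratum mapping, and SAP 9 does not list one as a change.

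**Futility rule for the low-CPS subgroup.** Under protocol 9.2, if at most one patient responds "in the first 10 patients enrolled in the combination arm for this subgroup, there will be no further enrollment in this subgroup". The rule comes from a "single arm BOP2 design with the interim assessment after 10 patients, a final assessment of 27 patients", "testing a null hypothesis of 15% ORR" against 29%, at a one-sided 10% level with about 65% power. Protocol 9.10.2 makes it non-binding. SAP 8 does not mention it.

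**Analyses.** The PFS log-rank test is "stratified for Baseline CPS category" (variable cpsgr1). The Cox model uses the same variable, and OS follows PFS. SAP 5.12.6 forms subgroups at CPS 20. The SAP does not say whether cpsgr1 holds the randomisation stratum or the measured value.

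**The concern.** The two documents give different sources for the stratum. Under the SAP, a patient can be randomised on TPS and later have a measured CPS on the other side of 20.

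The direction of error depends on how the scores relate, and neither document defines them. On the usual definition, CPS counts the stained tumour cells that TPS counts plus stained immune cells, over the same denominator, so CPS is at least TPS. On that assumption a TPS of 30 to under 50 means a CPS of at least 30, and the mapping misplaces all such entrants in one direction: higher expressers go into the low stratum. Entrants with TPS of 50 or more are placed correctly.

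Two things are then at stake:

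- **The futility rule.** If the first ten patients are identified by randomisation stratum, higher-expressing patients add responses to a count meant to judge CPS 1 to under 20. The rule then stops less often when that subgroup is doing no better than 15%.
- **The CPS analyses.** The stratified PFS and OS comparisons and the CPS subgroup results depend on which value is used, and the SAP leaves this to the programmer.

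**Working it through.** **Inputs**

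- Rule: close the subgroup at 1 or fewer responses in 10; final size 27; 15% versus 29%; one-sided 10%; about 65% power (protocol 9.2).
- Low-CPS ORR, pL: 15% or 29% (the same section).
- ORR of a misplaced patient, pH: 23%, pembrolizumab alone in CPS 20 or higher (protocol 1.1.1); 33% to 43%, danvatirsen plus durvalumab in CPS 20 or higher (protocol 1.1.2).
- Number misplaced among the ten, k: not in the documents, so varied from 0 to 4.

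**Step 1: reproduce the plan's figure.** The final cut-off is not stated. Let x be the responses in the first 10 patients. With success at r or more responses in 27,

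P(success) = sum over x = 2 to 10 of Bin(x; 10, p) × P(Bin(17, p) ≥ r − x).

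- r = 6 gives 16.9% at p = 15%, above the 10% limit.
- r = 7 gives 8.6% at 15% and 65.1% at 29%.

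So r = 7 is the smallest cut-off that holds the 10% level, and it reproduces the stated power of about 65%.

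**Step 2: closure probability with nobody misplaced.**

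- At 15%: 0.85^10 + 10 × 0.15 × 0.85^9 = 0.197 + 0.347 = 54.4%.
- At 29%: 0.71^10 + 10 × 0.29 × 0.71^9 = 0.033 + 0.133 = 16.6%.

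**Step 3: closure probability with k misplaced, if the count follows the randomisation stratum.**

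P(close) = (1−pL)^(10−k) (1−pH)^k + (10−k) pL (1−pL)^(9−k) (1−pH)^k + k pH (1−pH)^(k−1) (1−pL)^(10−k)

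For k = 2, pL = 0.15, pH = 0.43:

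- no responses: 0.85^8 × 0.57^2 = 0.0885
- one response, in a low-CPS patient: 8 × 0.15 × 0.85^7 × 0.57^2 = 0.1250
- one response, in a misplaced patient: 2 × 0.43 × 0.57 × 0.85^8 = 0.1336
- total 0.347

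Results at pL = 15%:

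| k of 10 | pH 23% | pH 33% | pH 43% |
|---|---|---|---|
| 0 | 54.4% | 54.4% | 54.4% |
| 1 | 51.5% | 47.8% | 44.1% |
| 2 | 48.6% | 41.6% | 34.7% |
| 3 | 45.8% | 35.8% | 26.7% |
| 4 | 43.1% | 30.6% | 20.2% |

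At pL = 29%, k = 2 moves closure from 16.6% to 18.6%, 15.2% or 12.1% for pH of 23%, 33% or 43%. The rule is therefore more lenient only when misplaced patients respond more often than the low-CPS patients they replace. The larger shifts occur when the subgroup is at its null rate.

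**Step 4: what the mapping does not touch.** TPS is known before randomisation and allocation is 2:1 in both strata. The primary ORR comparison (posterior rule in protocol 9.2 and SAP 8; Fisher's exact test in SAP 5.12.2) uses no strata.

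**The case against.** The strongest reply is that the documents do not show any harm. CPS being at least TPS is not stated in them. Inclusion criterion 5 names four assays and accepts any pre-treatment tissue sample for CPS, so the two scores need not share an assay or specimen in every patient. The futility rule is worded by CPS, and a CPS value is mandatory, so the natural reading is that measured CPS decides who is counted. The rule is also non-binding. The PFS and OS analyses already name baseline CPS category, and SAP 5.12.7 treats secondary endpoints as descriptive. A difference between the randomisation stratum and measured CPS is not a fault in itself: analysing by measured CPS keeps that difference for anyone randomised on TPS.

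Most of this stands, and it limits the point. A reader might infer that the randomisation is compromised, that the futility count was in fact distorted, or that half the trial depended on it. The documents do not support these readings. Allocation is intact, so the cost is some loss of CPS balance. No counting rule is given in either direction. The 27 patients are half of the intended combination arm (27 of 54), used to derive the rule, and are not a quota for the subgroup.

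What the reply does not remove is the conflict between SAP 4 and 5.3 and protocol 3.4, which needs no outside definition. It also leaves unanswered which value governs when the two disagree.

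**Conclusion.** The point holds as a conflict between the documents and an unspecified definition. The SAP's mapping departs from the protocol's stratification on screening CPS without explanation. Assuming CPS is at least TPS for the same specimen and assay, it places every entrant with TPS 30 to under 50 in the wrong stratum.

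The effect on the futility rule is conditional on counting by randomisation stratum. With a true low-CPS ORR of 15% and two of ten misplaced, the chance of closure falls by 5.8 to 19.7 percentage points (54.4% to between 48.6% and 34.7%). With no TPS entrants among the ten, or with counting by measured CPS, it does not change. The documents do not say which case applies.

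The validity of randomisation and the error rates of the primary ORR analysis are not affected. SAP 9 reports early termination, so changes to the randomisation system and the accrual rule have little prospective effect. The definition of CPS in the analyses and the report still matters.

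**What to change.** 1. Reconcile SAP 4 and 5.3 with protocol 3.4 by assigning the stratum from the CPS measured at screening. Sending every entrant with TPS of 30 or more to the CPS 20 or higher stratum is not a substitute, because it rests wholly on a scoring relation the documents do not state. If patients were randomised under the mapping, record this in SAP 9.
2. State in the SAP that the CPS 1 to under 20 futility count, cpsgr1 and the CPS subgroups all use measured pre-treatment CPS. Add a rule for values that arrive late or disagree with the assigned stratum.
3. Add one table of randomisation stratum against measured CPS, by arm. It gives the missing number of misplaced patients, and so shows which row of the scenarios above applies.

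Cost: items 2 and 3 need a few SAP sentences and one table from data already required. Item 1 could bring a short delay while CPS is read before randomisation. With the study ended early, items 2 and 3 are the part to carry out.

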## 5 PLANNED ANALYSES

The Statistical Analysis Plan (SAP) and Table, Figure, Listing (TFL) Shells (and any amendments) must be approved prior to database lock. If post database lock, additional statistical analyses or changes to the statistical analysis are required, then those will be documented in a Post Database Lock Statistical Analysis Plan Addendum.

### 5.1 Analysis Sets

Analysis Set	Description
Full Analysis Set (FAS)	All randomized patients who receive at least 1 dose of study treatment based on the treatment assigned at randomization.  The FAS will be the primary analysis set for efficacy analyses.
Safety Analysis Set	The Safety Analysis Set (SAS) is defined as all patients who receive at least 1 dose of study treatment based on the actual treatment received.  The Safety Analysis set will be the primary analysis set for safety analyses.
Pharmacokinetic (PK) Analysis Set	The PK Analysis set is defined as all FAS patients with evaluable PK data. Additional details are outlined in the PKAP.
Biomarker Analysis Set	All FAS patients with evaluable biomarker data.

### 5.2 Derived Data

This section describes the derivations required for statistical analysis. Unless otherwise stated, variables derived in the source data will not be re-calculated.

#### 5.2.1 Race

Where more than one race category has been selected for a patient, these race categories will be combined into a single category labelled “Multiple Race” in the summary tables. The listings will reflect the original selected categories.

#### 5.2.2 Baseline

Baseline is defined as the last non-missing value (either scheduled, unscheduled or repeat) before the patient receives the first dose of study drug.

QMD Ref: Worldwide-TMP-ST-054-1.0_Effective: 12Aug2022	Governing QMD: Worldwide-SOP-ST-026
Confidentiality Statement	

This document is the property of Worldwide Clinical Trials Inc. and may not be duplicated, copied, altered or removed from company without prior approval from Worldwide Quality Assurance or in compliance with Worldwide Standard Operating Procedures.

Worldwide Clinical Trials Controlled Quality Management Document			
 WORLDWIDE CLINICAL TRIALS	Sponsor:	Flamingo Therapeutics	
	Protocol Number:	FLM-6774-201	
STATISTICAL ANALYSIS PLAN			

### 5.2.3 Change from Baseline

Change from Baseline to post-Baseline visit/timepoints will be calculated as follows.

$$\text{Change from Baseline} = \text{Post-Baseline Value} - \text{Baseline Value}$$

If the Baseline value is missing, then change from Baseline will be left as missing.

### 5.2.4 Study Day and Duration

Study day will be calculated as the number of days from the first dose of study treatment as follows.

For events on or after the first dose of study treatment:

$$\text{Study Day} = \text{Date of Event} - \text{Date of 1}^{\text{st}} \text{ Dose} + 1$$

For events before the first dose of study treatment:

$$\text{Study Day} = \text{Date of Event} - \text{Date of 1}^{\text{st}} \text{ Dose}$$

The duration of an event will be calculated in days as follows.

$$\text{Duration} = (\text{Stop Date} - \text{Start Date} + 1)/365.25.$$

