Each AE will be evaluated for duration, severity according to the CTCAE v5.0, seriousness, and causal relationship to each study treatment. The action taken with each study treatment and the outcome must also be recorded.

All SAEs, regardless of relationship to each study treatment, must be reported immediately (within 24 hours of awareness of event by Investigator) to the Sponsor and contract research organization (CRO) pharmacovigilance group. All SAE notifications should be made by completing the AE eCRF in the electronic data capture (EDC) system. Follow-up SAE reports must be submitted by the Investigator as new information becomes available.

The Medical Monitor for this study may be contacted for advice or assistance. Contact details will be provided separately in a study contact list.

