### 5.2.5 Conventions for Missing and Incomplete Dates

All dates in the individual subject listings will be presented exactly as recorded on the Electronic Case Report Form (eCRF).

Historical dates, such as the start and stop of concomitant medication and medical history, will not be imputed if missing or incomplete.

Imputation of dates for adverse events with incomplete dates will be performed only for determination of treatment emergence and for the calculation of adverse event duration. Imputed dates will not be presented in data listings. The following algorithm will be used to estimate adverse event start dates for which only partial information is known:

- Completely Missing
  - Earliest of date of first dose of study drug or imputed stop date.
- Missing day and month only
  - If the year is same as the year of first day on drug, then the day and month of the start date of drug will be assigned to the missing fields.
  - If the year is prior to the year of first day on drug, then December 31 will be assigned to the missing fields.
  - If the year is after the year of first day on drug, then January 1 will be assigned to the missing fields.

QMD Ref: Worldwide-TMP-ST-054-1.0_Effective: 12Aug2022	Governing QMD: Worldwide-SOP-ST-026
Confidentiality Statement	
This document is the property of Worldwide Clinical Trials Inc. and may not be duplicated, copied, altered or removed from company without prior approval from Worldwide Quality Assurance or in compliance with Worldwide Standard Operating Procedures.	

Worldwide Clinical Trials Controlled Quality Management Document			
 WORLDWIDE CLINICAL TRIALS	Sponsor:	Flamingo Therapeutics	
	Protocol Number:	FLM-6774-201	
STATISTICAL ANALYSIS PLAN			

- Missing month only
  - Treat day as missing and replace both month and day according to the above procedure.
- Missing day only
  - If the month and year are same as the year and month of first day on drug, then the start date of drug will be assigned to the missing day.
  - If the month and year are before the year and month of first day on drug, then the last day of the month will be assigned to the missing day.
  - If the month and year are after the year and month of first day on drug, then the first day of the month will be assigned to the missing day.

If the AE stop date is complete and the imputed start date as above is after the stop date, the start date will be imputed using the stop date.

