### 5.2.10 Exposure to Study Drug

A Danvatirsen dose will be considered delayed if it is administered 11 to 14 days after the last dose and skipped if administered 15 to 21 days from the last dose. A second skipped dose will be counted if Danvatirsen is administered 22 to 28 days after the last dose, and so on.

A Pembrolizumab dose will be considered delayed if it is administered 25 to 42 days after the last dose and skipped if administered 43 or more days from the last dose.

Relative Dose Intensity (%) will be calculated separately for Danvatirsen and Pembrolizumab as the actual cumulative dose on study relative to the expected cumulative dose on study, assuming that no doses were missed or reduced. The following formula will be used.

$$\text{Relative Dose Intensity} = \text{Actual Cumulative Dose} / \text{Expected Cumulative Dose} \times 100$$

Actual cumulative dose (mg) for Danvatirsen is calculated as the cumulative sum of Calculated Dose as collected on the CRF during the study. Actual cumulative dose (mg) for Pembrolizumab is calculated as the cumulative sum of Dose as collected on the CRF during the study.

Expected cumulative dose (mg) for Danvatirsen for subjects that have completed at least 1 week of study drug is defined as follows.

$$\text{Expected Cumulative Dose} = (6 + 3 \times \text{Number of Weeks on Study}) * \text{kg}$$

For subjects that discontinued the study before completing 1 week on study, the expected cumulative dose (mg) is 3 mg/kg at day 1, 6 mg/kg at day 3, and 9 mg/kg at day 5.

Expected cumulative dose (mg) for Pembrolizumab is defined as follows.

$$\text{Expected Cumulative Dose (mg)} = 200 \text{ mg} \times \text{Every 3 Weeks on Study}$$

Treatment Duration for Pembrolizumab will be calculated in months as follows.

$$\text{Treatment Duration} = (\text{Date of Last Dose} - \text{Date of First Dose} + 1) / 30.4375$$

Treatment Duration for Danvatirsen will be calculated in months as follows.

$$\text{Treatment Duration} = (\text{Date of Last Dose} - \text{Date of First Dose} + 1) / 30.4375$$

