#### Surgical History

- Extent of Resection
- Time from Surgery (years).

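### SAP 5.2.4 labels event duration as days but divides by 365.25, which gives years: a minor derivation error to correct before adverse event durations are programmed

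*SAP*

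**What the plan says.** SAP 5.2.4 first defines study day by simple date subtraction. It then turns to event duration: "The duration of an event will be calculated in days as follows". The formula given is (stop date − start date + 1) divided by 365.25.

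SAP 5.2.5 makes AE duration a planned derivation. Imputation of incomplete AE dates "will be performed only for determination of treatment emergence and for the calculation of adverse event duration". Protocol 7.9.6 also names duration among the attributes of each event: "Each AE will be evaluated for duration, severity according to the CTCAE v5.0, seriousness, and causal relationship to each study treatment".

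Other durations have formulas of their own. In SAP 5.2.10, "Treatment Duration for Danvatirsen will be calculated in months as follows", with divisor 30.4375, and pembrolizumab is handled in the same way. DOR, PFS and OS (SAP 5.12.4.2 to 5.12.4.4) are also in months with divisor 30.4375. One item in the surgical history summary (SAP 5.8) is meant to be in years, "Time from Surgery (years)", and the SAP gives no formula for it.

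**The concern.** The sentence and the formula in SAP 5.2.4 cannot both be right. A programmer who follows the formula and keeps the stated unit will produce AE durations labelled as days that are really fractions of a year. A programmer who follows the stated unit will leave out the divisor. The SAP gives no rule for choosing between them, and this is the only event-duration formula available.

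What is at stake is the AE duration variable in the analysis datasets, and the AE listing if it carries that variable. Anyone reading those values as days, or reusing them in a later safety analysis, would be misled about how long events lasted.

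**Working it through.** **Inputs**
- Stated unit: days (SAP 5.2.4).
- Formula: (stop − start + 1)/365.25 (SAP 5.2.4).
- Comparison divisor: 30.4375, used with months in SAP 5.2.10 and 5.12.4.2 to 5.12.4.4.
- Event lengths of 1, 7, 10, 14, 30, 90 and 365 days. These are illustrative and do not come from the documents.

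**Step 1: unit check.** Let d = stop − start + 1. An event that starts and stops on the same date has d = 1, so d is the inclusive number of days. Dividing by 365.25 days per year gives years.

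**Step 2: the formula as written.**

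| True length d (days) | d/365.25, labelled days | Ratio |
|---|---|---|
| 1 | 0.0027 | 365.25 |
| 7 | 0.0192 | 365.25 |
| 10 | 0.0274 | 365.25 |
| 14 | 0.0383 | 365.25 |
| 30 | 0.0821 | 365.25 |
| 90 | 0.2464 | 365.25 |
| 365 | 0.9993 | 365.25 |

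The ratio does not depend on the length of the event.

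**Step 3: could a different divisor rescue the label?** No. With the month divisor used elsewhere, 30/30.4375 = 0.986 and 90/30.4375 = 2.957, which are months. Only d itself, with no divisor, is in days.

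**Step 4: is the mismatch general?** No. Since 365.25/12 = 30.4375, the formulas for treatment duration, DOR, PFS and OS convert days to months and are labelled months. Unit and divisor agree in all of them. Only SAP 5.2.4 fails.

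**Step 5: which outputs could carry the error?** The AE summaries in SAP 5.13.1 are numbers of subjects and events by system organ class and preferred term, relationship, seriousness, action taken, death and grade. None reports duration. The list of tables, figures and listings in SAP 11 has no title for AE duration. Two places remain: the analysis datasets, and AE listing 16.2.7.1, whose columns are not shown in either document.

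**The case against.** The strongest reply is that this is a slip in a label with no visible result behind it. If years were intended, the numbers are right and only one word is wrong. No planned table or figure shows AE duration, and no endpoint or decision rule uses it. All of that stands, and it is why the point is minor. It does not remove the contradiction, because one of the two elements has to change under either reading.

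A reader might infer more from the error than the documents support:

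- **That reported safety results would be wrong 365-fold.** The planned safety tables contain no AE duration, so none of them would change.
- **That derived durations could not be set against the protocol's 21-day (danvatirsen) and 42-day (pembrolizumab) periods for recovery from toxicity.** Investigators apply those periods at the site during treatment (Protocol 5.4.1). Neither document plans to compare them with a derived AE duration.
- **That long events would look as if they had resolved at once.** SAP 5.2.5 shows dates in subject listings as recorded on the eCRF. A listing with start and stop dates would expose a value of 0.08 days beside a month-long event.
- **That independent double programming will reproduce the error.** It might. But the instruction contradicts itself, so two programmers may resolve it differently and the mismatch would then surface. SAP 11 also calls for manual review of format.
- **That the protocol sentence on evaluating each AE for duration ties the formula to a result.** That sentence is in the AE reporting section and concerns assessment and recording of events. It specifies no statistic.

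**Conclusion.** The inconsistency is certain: SAP 5.2.4 pairs the unit days with a formula that gives years, and nothing elsewhere in either document corrects it. The understatement by a factor of 365.25 is conditional. It arises only if the formula is programmed as written and the output carries the SAP's own label. If the output were labelled years, the values would be correct.

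Days is the better-supported reading for events. The text says so, and the study day formulas directly above are in days. The 365.25 divisor would suit time from surgery, which is to be reported in years and has no formula of its own. The documents do not settle what was intended.

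The effect is confined to the AE duration variable in the analysis datasets and, if it shows duration, listing 16.2.7.1. ORR, DOR, PFS, OS, treatment duration and treatment-emergent AE counts are unaffected. This is a minor derivation error, worth correcting because the rule as written gives a wrong value and the correction is trivial.

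**What to change.** In SAP 5.2.4, replace the formula with: Duration (days) = stop date − start date + 1. Where a quantity is reported in years, such as time from surgery, add a separately labelled formula with the 365.25 divisor. If the sponsor did intend event duration in years, keep the formula and change the word days to years.

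The cost is one line in the SAP, plus one more for the years formula. SAP 5 requires amendments to be approved before database lock and sends later changes to an addendum. SAP 9 says that early termination brings the final analysis forward. The edit is therefore best made now, together with a check that any AE duration already programmed, and its label in listing 16.2.7.1 if shown, use the corrected definition.
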